### **11.14.2 Selection of Investigators**

Acutus Medical will select Investigators (including Sub Investigators performing the procedure) qualified by training and experience. Sites will be selected based on a site assessment, appropriate facilities, clinical experience and the qualifications of the Principal Investigator. Investigators will be evaluated by Acutus Medical based on:

- Curriculum vitae, or other statement of Investigator's relevant training and experience, including type of experience with the intended procedure and clinical research, specifically
- Education and experience in the ablation management of arrhythmias
- Whether the Investigator has an adequate patient population to meet requirements of the study enrollment
- Whether the Investigator has adequate time to be personally involved in the conduct of the study, and adequate research staff and resources to support the study
- Whether the Investigator's Study Center is associated with an EC that satisfies all applicable regulatory requirements
- Whether an Investigator was involved in an investigation or other research that was terminated. This may require an explanation of the circumstances that led to the termination.

Prior to study initiation, each Investigator must also submit a:

- Certificate of human patient's protection training (if required by the reviewing EC),

- Signed Investigator's Agreement, indicating an Investigator's commitment to:
  - Conduct the investigation in accordance with the agreement, the Clinical Investigational Plan/protocol, GCP, and any conditions of approval imposed by the EC;
  - Supervise all testing of the device involving human subjects;
  - Ensure that the requirements for informed consent are met;
  - Conduct the study according to the Clinical Investigational Plan/protocol.

The Sponsor reserves the right to apply additional criteria to site and/or Investigator selection.

### **11.15 Training**

Acutus Medical will provide training on the AcQMap™ System **prior** to enrolling any subject. Training may consist of a review of the IFU, hands-on training on the device and procedure, presentations, literature, etc. The training program will be standardized and will be documented. Additional training will include a review of the protocol, the regulations for medical device investigations and general study logistics required to complete the study.

Training of appropriate clinical study personnel will be the responsibility of Acutus Medical. To ensure uniform data collection and protocol compliance, Acutus Medical will review the Clinical Investigational Plan/protocol (including the ICF), techniques for identification of eligible subjects, instructions on data collection, methods for scheduling follow-up visits in the window, etc. Detailed feedback regarding completion of the eCRFs, study requirements, and protocol compliance will be provided by Acutus Medical, its study monitors, and/or designees, functioning in a data management capacity.

#### **11.15.1 Changes in the Clinical Investigational Plan**

Acutus Medical will obtain appropriate regulatory approval for any change to the Clinical Investigational Plan/protocol that may affect the scientific soundness of the investigation or the rights, safety and/or welfare of the subjects.

Acutus Medical will provide approved protocol amendments to the Investigators prior to implementing the amendment. The Investigator will be responsible for notifying the reviewing ECs of the protocol amendment (administrative changes) or obtaining

EC approval of the protocol amendment (changes in subject care of safety), according to the instructions provided with the protocol amendment. The EC acknowledgement/approval of the protocol amendment must be documented in writing prior to implementation of the protocol amendment. Copies of this documentation must be provided to Acutus Medical and placed in the Trial Master File (TMF).

#### **11.15.2 Withdrawal of Regulatory Approval**

Acutus Medical will notify all reviewing ECs and participating Investigators of any withdrawal of regulatory approval to conduct the clinical study, and shall do so within five (5) business days after receipt of notice of the withdrawal of approval.

### **12 ETHICS AND REGULATORY COMPLIANCE**

#### **12.1 Conduct of the Clinical Study**

Conduct of the clinical study will follow QAPs from Acutus Medical, as well as the Declaration of Helsinki, Good Clinical Practices, ISO 14155: 2011, and other regional and local laws. Each Investigator must sign and date the Investigator Agreement prior to the start of this study. With the signature, the Investigator agrees to perform all study procedures according to the governing local and national regulations and the Clinical Investigational Plan Protocol.

#### **12.2 Ethics Committee Approval**

A properly constituted, valid Ethics Committee (EC) must review and approve the Clinical Investigational Plan (CIP), Informed Consent, and related patient information and recruitment materials prior to initiation of the study. It is the responsibility of the Investigator to obtain protocol approval from the institution's EC, and to keep the EC informed of any serious adverse events or serious adverse device effects and amendments to the protocol. Additional requirements imposed by the EC or other regulatory authority shall be followed as appropriate. All correspondence with the EC should be filed by the Investigator and copies sent to Acutus Medical (or designees).

#### **12.3 Clinical Study Informed Consent Approval**

In accordance with the principles of Informed Consent, the Declaration of Helsinki, Good Clinical Practice (GCP), and ISO 14155: 2011, informed consent will be obtained and documented in writing before a patient is enrolled in the clinical study.

It is the responsibility of the Investigator to ensure that a written informed consent is obtained from the patient (or legally acceptable representative) before any activity or procedure is undertaken that is not part of routine care. Information obtained during

the conduct of the clinical study that may impact the patient informed consent may require revisions to the informed consent. If so, revisions and approvals of such changes by the appropriate regulatory authority is required. Documentation of the current versions of the informed consent will be documented in the clinical study TMF.

#### **12.4 Identification and Confidentiality**

Patient identification and confidentiality will be ensured in accordance with all applicable regulatory and Ethics Committee governance. This includes, but is not limited to, the following:

- Subjects will be identified on all eCRFs and source documents by a unique identification reference
- eCRFs are confidential documents and will only be made available to Acutus Medical (and appropriate designees), the Investigator, the biostatistician, the Clinical Events Committee (CEC), and, if requested, to advisory committees and regulatory authorities (including USFDA)
- Data will be stored and analyzed by computer following national regulations for handling of computerized data

Each Study Center will maintain (anonymous to Acutus Medical) a list identifying all patients entered into the trial. The list will be maintained as part of the investigation file and monitored for completeness.

#### **12.5 Site Qualification Visits**

A site qualification visit will be performed to evaluate site facilities, Investigator qualifications, and site knowledge of Good Clinical Practice (GCP) guidelines. Acutus Medical's QAP for site qualification visits will be followed and a report filed in the Trial Master File (TMF), which will be maintained by Acutus Medical.

#### **12.6 Site Initiation Visits**

All study personnel will be required to participate in a site initiation visit that follows Acutus Medical's QAP. Components of this initiation visit may include:

- Introduction of the study design including the protocol-specific treatment and follow-up phase
- Informed Consent process
- Product training to all end-users
- eCRF completion training

- Safety reporting instructions
- Training on the regulations governing human research
- Procedure training on the use of the device

## **12.7 Insurance**

Acutus Medical shall maintain insurance coverage for this study. Pertinent information regarding the coverage shall be made available to the site upon request.

## **12.8 Site Audit Plan**

Participation as an Investigator in this study implies acceptance of potential inspection by government regulatory authorities and applicable compliance and quality assurance offices. The Investigator and/or designee must be available to respond to reasonable requests and queries made by authorized regulatory representatives during the audit process. The Investigator must provide Acutus Medical with copies of all correspondence that may affect the review of the current study or their qualifications as an Investigator in this and future clinical studies conducted by Acutus Medical.

### **12.8.1 Site Data Audits by Acutus Medical**

In accordance with local and national regulations and Acutus Medical's operating procedures, an internal audit may be requested to access all study records, including source documents, for inspection and duplication. The investigator will ensure the capability for inspections of applicable study-related functions.

Site data quality assurance audits may be conducted at various sites during the clinical study. Selection of sites to undergo auditing will be determined by the Acutus Medical as needed.

### **12.8.2 External Audits**

Requests by regulatory agencies to inspect the study sites may be made as well. The Investigator and/or designee is required to report to Acutus Medical as soon as possible after receiving a request from a regulatory authority to perform an audit. The clinical Investigator agrees to allow inspectors from regulatory agencies to review records, and to assist the inspectors in their duties, if requested.

## **12.9 Investigational Device Traceability**

The AcQMap™ System components will be stored at each site. All sites will maintain a device accountability log that will match patients to a particular device by a unique manufacturer number. At the conclusion of the study all unused devices will be returned to Acutus Medical.

## **12.10 Public Domain Access to the Clinical Study**

A description of this clinical trial will be available on <http://www.Clinicaltrials.gov>. Information regarding the public access will be presented in the informed consent.

## **12.11 Required Reports**

Acutus Medical will remain in compliance with all required and pre-specified reports during the enrollment and follow-up of the clinical study. EC requirements for reports, including minutes from CEC meetings, will be provided as requested.

# **13 GENERAL CONSIDERATIONS**

## **13.1 Discontinuation of the Clinical Study**

The Sponsor reserves the right to discontinue the study at any stage, with suitable written notice to the Investigator and the appropriate government regulatory agencies. Such decisions will be based on advice from the Scientific Advisory Board or Clinical Events Committee. Similarly, Investigators may withdraw from the study, subject to providing written notification to the Sponsor within 30 days of their intent to withdraw. However, the Sponsor and Investigators will be bound by their obligation to complete the follow-up of subjects already enrolled into the study.

Acutus Medical, as Sponsor, may terminate Investigator and site participation in the study if there is evidence of an Investigator's failure to maintain adequate clinical standards or evidence of an Investigator's or staff's failure to comply with the Clinical Investigation Plan/protocol.

Notification of suspension or termination will occur no later than five (5) business days after Acutus Medical makes the determination. In the event of study suspension or termination, Acutus Medical or designee will send a report outlining the circumstances to the reviewing EC, the appropriate regulatory agencies, and to all participating Investigators. Any suspension or termination may not be re-initiated without prior approval of the EC and Acutus Medical.

## **13.2 Use of Information and Publications**

All information concerning Acutus Medical operations, patent applications, manufacturing processes, and basic scientific data supplied by Acutus Medical to the Investigator and not previously published, are considered confidential and remain the sole property of Acutus Medical. This includes all study materials, CRF forms, worksheets and eCRFs.

The information developed in this study may be used by Acutus Medical as support for a regulatory filing and in connection with the continued development of the AcQMap™ System. Any publication or other public presentation of the data resulting from this study will require prior review and written approval of Acutus Medical.

At the conclusion of the study, it is expected that Acutus Medical and the Investigators will promptly prepare and submit a multi-center manuscript for publication in a reputable scientific journal. The publication of the principal results, including abstracts, from any single-site experience within the study is not allowed until the preparation and publication of the multi-center results. Exceptions to this rule require the prior written approval of Acutus Medical.

Further analyses, beyond those presented in the initial multi-center publication may be proposed to Acutus Medical. Many secondary manuscripts are anticipated. For purposes of timely abstract presentation and publication, such secondary publications may be delegated to the appropriate principal authors; however, final analyses and manuscript review for all multi-center data will require the prior written approval of Acutus Medical.

None of the results, in whole or part, of the study carried out under this protocol, nor any of the information provided by Acutus Medical for the purposes of performing the study, will be published or passed on to any third party without the consent of Acutus Medical. Any Investigator involved with this study is obligated to provide Acutus Medical with complete test results and all data derived from the study.

## **14 APPENDIX**

### **14.1 Bibliography**

A bibliography of pertinent publications identified or supportive of the clinical study will be maintained by Acutus Medical and available upon request.

**STATKING Clinical Services**

## Revision History

### Version 1.1 to 2.0

1. Listing 6 (AEs): modified to add columns specifying device relationship to AE for each device.
2. Listing 15 (Catheter Data): Part 5 header corrected. Part 4 Sheath Model number and Lot number added.
3. Listing 16 (PVI Data): Column added to identify visit and PVI count.
4. Table 2 and Time-to-event specification: TTE defined as  $TTE = \text{End-Date} - \text{Start-Date}$  rather than  $\text{End-Date} - \text{Start-Date} + 1$ .
5. Tables 7 and 35: Footnote added to state data source as continuous monitor data with 12 lead imputation when continuous monitor data are unavailable.
6. Table 16: Highest Relationship to Device expanded to summarize relationships to System, Catheter, Sheath, and PEK (in accord with added tables 20- 22).
7. Tables 16, 17, 18, 19 (AEs): Table sources modified to use CEC adjudication only, titles changed to reflect this. Text of Section 4.2.2 changed to reflect these changes.
8. Table 19 (AE Relationship to Device) – Changed to Relationship to AcQMap Catheter.
9. Tables 20-22 – Added to summarize additional AE relationship assessments.

### Version 1.0 to Version 1.1

1. In Appendix B, the shell for Table 6 modified to include Total Procedure Time.
2. In Appendix B, the shell for Table 7 extensively modified to add AF only subtables. It is split into Table 7 (AF, AFI, and AT) and Table 32 (AF only). A complete list of the subtables is given below (*italics* represent current subtables):

#### Table 32 (New)

- a. Freedom from AF with a single procedure.
- b. Freedom from AF with a single procedure without AADs.
- c. Freedom from AF with a single procedure with AADs.
- d. Freedom from AF with multiple procedures.
- e. Freedom from AF with multiple procedures without AADs.
- f. Freedom from AF with multiple procedures with AADs.

#### Table 7 (Existing)

- g. *Freedom from AF/AT/AFL with a single procedure.*
- h. *Freedom from AF/AT/AFL with a single procedure without AADs.*
- i. *Freedom from AF/AT/AFL with a single procedure with AADs.*
- j. *Freedom from AF/AT/AFL with multiple procedures.*
- k. Freedom from AF/AT/AFL with multiple procedures without AADs.
- l. Freedom from AF/AT/AFL with multiple procedures with AADs.

3. Imputation of 12-Lead ECG rhythm for missing Holter data added to Appendix B. Table 22 divided into three parts to display 12-lead results at baseline, 1, 3, 6, and 12 months, Holter monitor data at 3, 6, 9, and 12 months, and results after imputation.
4. Appendix B. Table 33 added to cover medical history co-morbidities.
5. Treatment Population redefined in terms of atrial mapping rather than sensor deployment.
6. Data Listing 2: Date-of-birth column removed, because it is not present in the data file.
7. AFEQT questionnaire scoring algorithms added to text.
8. Data Listing 15 divided across 5 pages (from 3) to reduce line breaks.

## 1.0 Synopsis of Study Design Procedures

This Statistical Analysis Plan (SAP) describes the analysis of data from Acutus Medical Studies CL-AF-001 and CL-AF-002, both referred to by the acronym UNCOVER-AF. The CL-AF-001 study is being conducted in Canada as a pre-market study, and the CL-AF-002 study is being conducted in Europe as a post-market study.

Data from both studies are considered suitable for pooling based on identical patient inclusion and exclusion criteria, procedures, and measurement methods for outcomes data. Moreover, the patients in the general population of the countries conducting the study have similar demographics. For the purposes of the analysis tables planned in this SAP, the data will be treated as data originating from a single study. Data listings will report the study number in order to identify the protocol under which each individual subject was enrolled.

Each study is a prospective, single-arm, multi-center, multi-national, non-randomized study designed to provide clinical data regarding the use of the AcQMap® System in the ablation of persistent atrial fibrillation (AF).

The objective of the statistical analyses is to evaluate the incidence of device- and procedure-related safety, efficacy, and efficiency (six and 12 month outcomes) when using the AcQMap as an imaging and mapping system for ablation of persistent AF.

### 1.1 Design and Treatment

Subjects will be enrolled in the trial for approximately 12 months. All enrolled subjects will undergo an ablation procedure using the AcQMap Imaging and Mapping System as the only advanced 3D navigation system. The AcQMap Imaging and Mapping System is intended for imaging and mapping of cardiac chambers, which will be utilized in the management of cardiac arrhythmias.

### 1.2 Study Procedures

Subject assessments will occur at screening, procedure, hospital discharge, one, three, six, nine, and 12 months. A follow up phone call will also occur seven days post-procedure.

Inclusion and exclusion criteria will be assessed prior to enrollment and during the screening period up through the pre-procedure required transesophageal echocardiogram (TEE). Assessments performed during screening will include subject demographics, medical history, physical exam findings, transthoracic echo (TTE) results (within previous six months), clinical laboratory exams, electrocardiograms (ECGs), the Atrial Fibrillation Effect on Quality of Life (AFEQT) questionnaire and the aforementioned TEE.

Subjects who meet all inclusion and exclusion criteria will be enrolled into the study and will proceed to receive an ablation procedure. Prior to hospital discharge, the following post-procedure evaluations will be completed: physical exam, 12-lead ECG, collection of concomitant medications and reporting of all adverse events. A phone call will occur seven days following hospital discharge to review concomitant medications, adverse events, and scheduled follow up visits.

Follow up clinical visits will occur at one, three, six, and 12 months. The following evaluations will be performed:

- History and physical exam (including neurological assessment)
- Medication history
- Adverse events assessment
- Vital Signs
- 12-lead electrocardiogram
- Echocardiogram (TTE at 12 months only, for comparison to baseline)
- AFEQT Questionnaire (completed prior to the clinic visit)
- 24-hour continuous monitor (three, six, nine, and 12 months post ablation procedure)
  - Since the 24-hour continuous monitor at nine months does not coincide with a follow-up visit, the subject will be instructed how and when to wear the recording device. Once the recording is completed, the device will be returned to a core lab. Results will be compiled and reported to the site and Sponsor. Results of the recording will be entered into an electronic case report form (eCRF).

### 1.3 Sample Size

The total sample size for the combined studies was selected based on the primary safety objective of the study. In order to estimate the primary safety objective within a margin of error of 3.89% (i.e., this is the 95% confidence interval half-width), assuming the observed proportion of subjects who are free from device/procedure related Major Adverse Events (MAEs) that occur within the first 24 hours post index procedure is 96.0%, a total of 125 subjects is required. These calculations assume the data are from a binomial distribution and that the confidence interval will be computed using the Clopper-Pearson exact approach.

## 2.0 Data Analysis Considerations

### 2.1 Types of Analyses

Data analyses will consist of descriptive statistics and confidence intervals. Tests of hypotheses will not be conducted.

## 2.2 Analysis Populations

The following analysis populations will be defined for the study:

**Safety Population** – The safety population will include all enrolled subjects who have the venous access portion of the ablation procedure initiated.

**Treatment Population** – The treatment population will include all enrolled subjects who complete a procedure up to the point the AcQMap catheter has completed mapping the atrial anatomy.

The analysis of the primary safety objective of the study will be based on the safety population. The analysis of the secondary safety and effectiveness outcomes will be based on the safety population or the treatment population as indicated in Sections 4 and 5 below.

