STUDY DURATION	Enrollment is anticipated to take approximately six (6) to eight (8) months. Post-procedure follow up will occur at hospital discharge, 1, 3, 6, and 12 months. The total study duration is anticipated to be approximately 18 months.
STATISTICAL METHODS AND ANALYSIS SUMMARY	
The primary outcome measure for the study is the primary safety objective, defined as the proportion of subjects who are free from device/procedure related Major Adverse Events (MAEs) that occur within the first 24 hours post-procedure. Subjects who remain free from such device/procedure related MAEs will be considered a success with respect to the primary safety objective, and subjects who experience at least one such MAE will be considered a primary safety failure.
 
The analysis of the primary safety objective will be performed on the treatment population, which will include all enrolled subjects who complete a procedure up to the point the AcQMap catheter is deployed in the left atrium. The number and proportion of subjects in the treatment population who are primary safety successes will be computed, along with a 95% exact binomial (i.e., Clopper-Pearson) confidence interval on the proportion.
 
Descriptive statistics will be applied to all other outcome measures.

FOLLOW-UP EVALUATIONS	See Table Below

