## **6.5 Clinical Study Enrollment Definitions**

For the purposes of this clinical study, the following definitions regarding the status of a subject will apply:

Screen Failure Subject – Any subject who has not met all of the inclusion and exclusion criteria. This includes a subject who may be excluded based on the results of the pre-procedure TEE. Screen failure subjects should have the screening eCRF completed and the screening data entered in the database.

Enrolled Subject – Any subject who has signed an informed consent form and is deemed study eligible by meeting all of the inclusion and exclusion criteria.

Pre-treatment Subject – Any enrolled subject who has the venous access portion of the ablation procedure initiated. Pre-treatment patients that do not complete the AcQMap procedure will be followed for adverse events through hospital discharge. In addition to the discharge eCRF, a study completion eCRF will be completed. No follow-up beyond the hospital discharge will be required.

Treatment Subject – Any pre-treatment subject who completes the ablation procedure to the point the AcQMap catheter and AcQGuide sheath has been deployed in the left atrium. Treatment subjects will be followed for all study outcome measures for the full duration of the clinical study. The number of treatment subjects will be used for the study sample.

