**Figure 2: Flow Diagram of Follow-Up and Retreatment Procedures**

## 8 STATISTICAL METHODS

### 8.1 Analysis Population

The following analysis populations will be defined for the study:

**Safety Population** – The safety population will include all enrolled subjects who have the venous access portion of the ablation procedure initiated.

**Treatment Population** – The treatment population will include all enrolled subjects who complete a procedure up to the point the AcQMap catheter is deployed in the left atrium.

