### 8.2 Statistical Analysis for Primary Safety Outcome Measure

The primary outcome measure for the study is the primary safety objective, defined as the proportion of subjects who are free from device/procedure related Major Adverse Events (MAEs), as adjudicated by the CEC, that occur within the first twenty-four (24) hours post-procedure. Subjects who remain free from such device/procedure related MAEs will be considered a success with respect to the primary safety objective, and subjects who experience at least one such MAE will be considered a primary safety failure. MAEs that occur during the first 24 hours will be reported and adjudicated by the CEC for any probable relationship to the device and/or procedure.

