#### 4.2 Analysis of Safety Objectives

##### 4.2.1 Analysis of Primary Safety Objective

Subjects who remain free from device/procedure related MAEs, as adjudicated by the CEC, that occur within the first twenty-four (24) hours post index procedure will be considered a success with respect to the primary safety objective, and subjects who experience at least one such MAE will be considered a primary safety failure. MAEs that occur during the first 24 hours will be reported and adjudicated by the CEC for any probable relationship to the device and/or procedure.

The analysis of the primary safety objective will be performed on the safety population. The number and proportion of subjects in the safety population who are primary safety successes will be computed, along with a 95% exact binomial (i.e., Clopper-Pearson) confidence interval on the proportion.

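### The protocol synopsis and the SAP name different populations for the primary safety analysis, and the two documents define the treatment population differently

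*Combined protocol and SAP*

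**What the plan says.** Population for the primary safety analysis:

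- Protocol synopsis, statistical methods row: "The analysis of the primary safety objective will be performed on the treatment population".
- SAP 4.2.1: "The analysis of the primary safety objective will be performed on the safety population". SAP 2.2 says the same.
- Protocol 8.2 defines the outcome ("subjects who experience at least one such MAE will be considered a primary safety failure") but names no population.

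Both documents define the safety population in the same way, from the start of venous access.

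Meaning of treatment population:

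- Protocol 8.1, and the synopsis in the same terms: enrolled subjects who "complete a procedure up to the point the AcQMap catheter is deployed in the left atrium". Protocol 6.5 uses the same point but adds the sheath.
- SAP 2.2: enrolled subjects who "complete a procedure up to the point the AcQMap catheter has completed mapping the atrial anatomy". The SAP revision history (version 1.0 to 1.1, item 5) records the change and gives no reason. The protocol supplied is the initial release and keeps the deployment definition.

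Use of the treatment population:

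- SAP 5.2.2 puts every secondary effectiveness analysis on it, and SAP 5.1.1 makes all effectiveness objectives secondary.
- SAP 4.2.2 puts all secondary safety analyses on it except treatment-emergent adverse events (TEAEs).
- Protocol 6.5: "The number of treatment subjects will be used for the study sample".

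**The concern.** The study has one primary endpoint and plans no hypothesis tests (SAP 2.1), so the proportion, its interval and its denominator are the result. Two current texts give different denominators, and the text supplied does not say which prevails.

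The subjects in dispute are those with venous access but no deployment. The MAE list includes perforation or tamponade and major bleeding, and procedure-related events count. A procedure could be stopped before deployment because of such an event. Under the SAP that subject is a primary failure; under the synopsis the subject is absent.

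The second conflict concerns subjects who had the catheter deployed but whose anatomy mapping was not completed. They have been exposed to the device and count toward the protocol's sample. Under the SAP they leave all the effectiveness summaries and the ECG, Holter, physical exam and vital sign summaries, because of something that happened after exposure. The text supplied plans no effectiveness analysis of all deployed subjects to set beside this.

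**Working it through.** **1. The plan's own figure.** Inputs from protocol 8.4 and SAP 1.3: N = 125, observed MAE-free proportion 96.0%, two-sided 95% Clopper-Pearson interval, half-width 3.89%. For x successes in n, the lower limit is the 0.025 quantile of Beta(x, n−x+1) and the upper limit is the 0.975 quantile of Beta(x+1, n−x). With x = 0.96 × 125 = 120, the limits are 90.91% and 98.69%, and the half-width is 3.89 points. The planned figure reproduces and is not in dispute.

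**2. Effect of the primary population, on assumed counts.** The documents do not say how many procedures stop before deployment. Assume 125 deployed subjects with 5 MAE failures (the planned 96.0%), plus k subjects with venous access but no deployment, f of whom have an MAE. The synopsis gives 120/125 whatever k and f are. The SAP gives (120 + k − f)/(125 + k).

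| k | f | SAP result | 95% CI (%) | Half-width (points) |
|---|---|---|---|---|
| 0 | 0 | 120/125 = 96.0% | 90.91–98.69 | 3.89 |
| 1 | 0 | 121/126 = 96.0% | 90.98–98.70 | 3.86 |
| 1 | 1 | 120/126 = 95.2% | 89.92–98.23 | 4.15 |
| 5 | 0 | 125/130 = 96.2% | 91.25–98.74 | 3.74 |
| 5 | 1 | 124/130 = 95.4% | 90.22–98.29 | 4.03 |
| 5 | 2 | 123/130 = 94.6% | 89.22–97.81 | 4.29 |

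If k = 0 the two analyses are identical.

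**3. When events start to count.** Naming the safety population does not quite settle step 2. The adverse event text under SAP 4.2.2 places the start of the ablation procedure, and so TEAE onset, at deployment in the left atrium. Protocol 7.3.2 measures procedure time from first venous access. SAP 4.2.1 does not restrict MAEs to TEAEs, so an MAE before deployment may count, but the SAP does not say that it does. A subject stopped before deployment has no procedure start under the SAP wording, yet is in the safety-population denominator.

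**4. Effect of the treatment-population definition, on assumed counts.** Suppose s of 125 deployed subjects succeed and k of the 125 did not complete anatomy mapping. Excluding them gives (s − k)/(125 − k) if all k had succeeded and s/(125 − k) if none had. Both values of s are assumptions: 84 for freedom from arrhythmia and 112 for acute procedural success.

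| k excluded | Freedom, 84/125 = 67.2% | Acute success, 112/125 = 89.6% |
|---|---|---|
| 0 | 67.2% | 89.6% |
| 1 | 83/124 to 84/124 = 66.9–67.7% | 111/124 to 112/124 = 89.5–90.3% |
| 2 | 82/123 to 84/123 = 66.7–68.3% | 110/123 to 112/123 = 89.4–91.1% |
| 6 | 78/119 to 84/119 = 65.5–70.6% | 106/119 to 112/119 = 89.1–94.1% |

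For scale, the full-set 95% intervals are 58.2–75.3% and 82.9–94.4%.

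**5. Follow-up wording in protocol 6.5.** One sentence reads "Pre-treatment patients that do not complete the AcQMap procedure will be followed for adverse events through hospital discharge"; another reads "Treatment subjects will be followed for all study outcome measures for the full duration of the clinical study". A subject deployed but not fully mapped has become a treatment subject, yet might be said not to have completed the AcQMap procedure. If such a subject left at discharge, the complete-case rule in SAP 2.3 would remove the subject from the 3 to 12 month rhythm results under either definition. Acute success and procedure times are recorded at or within 12 hours of the procedure, so their denominators depend on the definition in any case.

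**The case against.** The strongest reply on the primary endpoint is that the SAP already does the right thing. It names the broader population twice, and protocol 8.2 does not contradict it. Only one synopsis sentence does. This stands, and it reduces the first conflict to correcting the protocol and stating when MAEs begin to count. A rule of precedence could also sit in front matter that was not supplied.

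On the second conflict, the redefinition was deliberate. Protocol 5.2 says rhythm outcomes may give insight into how well the system identifies ablation targets, and a subject without a completed map says little about that. A mapped set is defensible for descriptive secondary outcomes, and the excluded subjects stay in the primary safety and TEAE analyses. This is a good reason to show the mapped set. It is not a reason to leave out the deployed set, or for one term to carry two meanings.

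A reader might infer that the SAP selects subjects on whether the device worked, and so inflates effectiveness. The documents do not support that. The SAP criterion is mapping of the atrial anatomy, whereas protocol 5.1 describes two outputs: the anatomical reconstruction and the dipole density maps placed on it. On the natural reading, a subject with completed anatomy but failed dipole density mapping stays in. Nor is it known whether excluded subjects would be failures; step 4 shows movement in both directions.

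A reader might also infer that protocol 6.5 releases deployed but unmapped subjects at discharge. The categories there are progressive, and the discharge sentence belongs to the pre-treatment category, so full follow-up is the better reading. What remains is a wording point.

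Finally, SAP Appendix B is not supplied and may already hold a disposition table. SAP 6.1 plans counts of completion and withdrawal, but not of the steps within the procedure.

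**Conclusion.** Both conflicts are certain as matters of current wording. For the primary endpoint, following the synopsis would omit MAEs in procedures stopped before deployment. For the effectiveness and non-TEAE secondary safety summaries, the SAP excludes, after device exposure, subjects whom the protocol counts in its sample.

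The size is not known. Neither group is counted in the documents, both may be empty, and the direction of any effect cannot be determined. On the assumed counts, the primary estimate moves from 96.0% to between 94.6% and 96.2%. Excluding up to six subjects moves freedom from arrhythmia by −1.7 to +3.4 points and acute success by −0.5 to +4.5 points. These shifts are small beside the sampling intervals, but an estimate lying inside an interval is not evidence that bias is absent.

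The point should be fixed because the estimates are the study's results and the correction is cheap. It does not show that any reported figure will be biased.

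**What to change.** 1. Amend the synopsis and protocol 8.2 to name the safety population for the primary analysis, as the SAP does.
2. State in both documents that MAEs from venous access onward count toward the primary endpoint, and reconcile this with the adverse event text in SAP 4.2.2, which starts the procedure and TEAEs at deployment.
3. Use one treatment-population definition in the synopsis, protocol 6.5 and 8.1, and SAP 2.2, including whether the sheath is part of it. Report effectiveness and non-TEAE secondary safety on the deployed-catheter set, scored by the existing endpoint definitions, with the mapping-completed set alongside.
4. Report counts and reasons at each step: venous access, catheter deployed, mapping completed.
5. As a minor point, reconcile the two follow-up sentences in protocol 6.5 so that it is clear which one covers a subject deployed but not fully mapped.

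The cost is wording in those sections, one disposition table (unless the unseen shells already have it) and one supporting analysis on data already collected. Figures may move slightly in either direction, or not at all if no such subjects exist.
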